3.4.4 Subgroups

The key study endpoints will be analyzed over time, including Forest plots, for the following subgroups of the FAS:

- Age (<65 years, \geq 65 years),

- Requirement for oxygen (Yes, No),
- Region (US, Ex-US),
- Baseline CRP (15-49, 50-100, >100 mg/L),
- Use of antivirals (Yes, No),
- Country.

3.5 Safety Assessment

3.5.1 Adverse Events (AEs)

The latest version of Medical Dictionary for Regulatory Activities (MedDRA) will be used for the coding of AEs.

Treatment-emergent AEs will be defined as an event that occurs on or after the first dose of study drug or the worsening of a preexisting condition on or after the first dose of study drug. If a subject does experience an event both prior to and after starting administration of a treatment, the event will be considered a TEAE (of the treatment) only if it has worsened (i.e., it is reported with a new start date and the event is worsened in severity or becomes serious) after starting administration of the specific treatment, and prior to the start of another treatment, if any. All TEAEs collected during the investigational period will be summarized.

A summary overview of TEAEs will be provided, which presents the number of events and the number and percentage of subjects in each treatment group from the Safety Analysis Set for each of the following categories:

- TEAEs (overall, by maximum severity, and by maximum drug relatedness)
- Study drug-related TEAEs (overall and by maximum severity)
- All treatment-emergent adverse events of special interest (AESI)
- All treatment-emergent serious AEs (TESAEs)
- All study drug-related TESAEs
- TEAEs leading to death
- TEAEs leading to study drug discontinuation
- Study drug-related TEAEs leading to study drug discontinuation
- TEAEs leading to study drug interruption
- Study drug-related TEAEs leading to study drug interruption

The number of TEAEs and the number of subjects with at least 1 TEAE will be summarized by treatment group for each of the categories in the overview.

All AEs will be displayed in listings. In addition, SAEs and TEAEs leading to study drug discontinuation will be listed.

3.5.2 Clinical Laboratory Tests

Reported values and change from baseline values of clinical laboratory variables will be summarized using descriptive statistics by treatment group and time point. The number of

available observations and out-of-range values (absolute and in percentage) will also be presented by treatment group. For out-of-range values summaries, all post-baseline values, including those from unscheduled visits will be evaluated.

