Based on the current safety and exposure information, dosing adjustment is likely not needed for subjects with renal insufficiency. However, close monitoring of pharmacokinetics (PK) for such cases will be implemented to ensure that therapeutic concentrations are maintained (refer to **Section 6.2**). For those subjects requiring dialysis, dose adjustment may be needed and will be determined by pre- and post-dialysis PK by the DMC. Adjustments may be recommended by the DMC also for subjects on placebo who develop acute renal failure to prevent unblinding at the sites.

Study treatment discontinuation

Discontinuation of study treatment should be considered if:

- ALT or AST >8 x the upper limit of normal (ULN)
- ALT or AST >5 x ULN for more than 2 weeks
- ALT or AST >3 x ULN and (total bilirubin >2 x ULN or international normalized ratio >1.5) in the absence of reasonable alternative etiology
- ALT or AST >3 x ULN with the appearance of fatigue, nausea, vomiting, right upper quadrant pain or tenderness, fever, rash, and/or eosinophilia (>5%)
- QTcF prolongation with QTcF >500 msec or an increase in QTcF of >60 msec over baseline (confirmed by 2 successive repeat measurements)

In addition, the investigator must permanently discontinue the study drug if continued administration of the study drug is believed to be contrary to the best interests of the subject. The premature discontinuation of study drug might be triggered by an adverse event (AE), a diagnostic or therapeutic procedure, an abnormal assessment (eg, ECG or laboratory abnormalities), pregnancy, or for administrative reasons, in particular noncompliance with the protocol or withdrawal of the subject's consent. The reason for study drug interruption or premature discontinuation must be clearly documented in the eCRF.

Fulcrum Therapeutics
Protocol FIS-001-2020

Losmapimod

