4.2 Exclusion criteria

1. Inability to take oral medication at screening or baseline visit.
2. Evidence at screening or baseline of critical COVID-19 disease (eg, cardiac failure, septic shock or ARDS) or immediate need for intubation or mechanical ventilation per the judgment of the investigator.
3. Positive pregnancy test at screening for women of childbearing potential.
4. Lactating female at baseline for women of childbearing potential.
 - a. Note: a female will be considered eligible who is lactating at screening if she agrees to discontinue breastfeeding for the duration of the trial plus 14 days post last dose.
5. $\geq 5 \times$ upper limit of normal (ULN) for alanine or aspartate aminotransferases or total bilirubin $>1.5 \times$ ULN at screening or known history of Child-Pugh Class C, hepatitis B or C, or poorly controlled HIV infection. (Subjects with HIV infection who have normal CD4 counts may participate if they have been on a stable antiviral regimen for the 30 days prior to screening and are anticipated to remain on the regimen throughout the duration of the study.)
6. Glomerular filtration rate $<30 \text{ mL/min/1.73 m}^2$ at screening.
7. QTcF $>450 \text{ msec}$ for male or $>470 \text{ msec}$ for females or evidence of cardiac dysrhythmia at screening.
8. Significant history or evidence of clinically significant disorder, condition, current illness, illicit drug or other addiction, or disease that, in the opinion of the Investigator, would pose a risk to subject safety or interfere with the study evaluation, procedures, or completion.
9. Has been treated with immunomodulators or immunosuppressants including, but not limited to, interleukin (IL)-6 inhibitors, tumor necrosis factor (TNF) inhibitors, anti-IL-1 agents, and Janus kinase inhibitors, within 5 half-lives or 30 days, whichever is longer, prior to randomization, or plan to receive these agents any time during the study period.
10. Treatment with hydroxychloroquine/ chloroquine in the past 30 days or plan to receive these agents as part of investigational clinical trials or SOC any time during the study period.
11. Recent (within 30 days) or current participation in other COVID-19 therapeutic trials or expanded access programs.
12. Prior or current participation in COVID-19 vaccine trials.

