6.5.5 Laboratory assessments

Laboratory parameters

Additional clinical laboratory evaluations will be performed at other times if judged to be clinically appropriate or if the ongoing review of the data suggests a more detailed assessment of clinical laboratory safety evaluations is required.

An Investigator (or designee) will perform a clinical assessment of all clinical laboratory data. Clinically relevant findings found after study drug initiation and meeting the definition of an AE (new AE or worsening of previously existing condition) must be recorded. Clinical relevance is defined as:

- Is accompanied by clinical symptoms
- Leads to dose modification of study treatment

Fulcrum Therapeutics
Protocol FIS-001-2020

Losmapimod

- Requires significant changes, addition of, interruption of, discontinuation of a concomitant medication, therapy, or treatment
- Reflects a disease and/or organ toxicity

This does not apply to any abnormal laboratory result that falls outside the laboratory reference range but that does not meet the clinical significance criteria or those that is a result of an AE that has already been reported.

Blood and other biological samples will be collected for the following clinical laboratory tests; refer to the Study Manual for details of collection and analysis and information on central and local laboratories:

Lab	Tests
Hematology	Hemoglobin [including mean corpuscular volume, mean corpuscular hemoglobin, mean corpuscular hemoglobin concentration], hematocrit, red cell count, total white cell count, and platelet count. Differential blood count, including: basophils, eosinophils, neutrophils, lymphocytes, and monocytes.
Chemistry and electrolytes	Sodium, potassium, calcium, inorganic phosphate, total protein, albumin, blood urea nitrogen, creatinine, uric acid, total bilirubin ¹ , alkaline phosphatase, AST, ALT, gamma-glutamyl transferase, and LDH.
Glucose	Glucose
Urinalysis	Leucocytes, blood, nitrite, protein, urobilinogen, bilirubin, pH, specific gravity, ketones, glucose. If there is a clinically significant positive result, urine will be sent for microscopy and/or culture.
Pregnancy ²	hCG (urine or serum). If there is a clinically significant, positive result in urine, urine will be sent for confirmation.

¹Conjugated bilirubin may be reported when total bilirubin is outside the reference range.

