7.1.2 Intensity of adverse events

The intensity of clinical AEs is graded 3-point scale as defined below:

- Mild: discomfort noticed but no disruption of normal daily activity;
- Moderate: discomfort sufficient to reduce or affect normal daily activity;
- Severe: inability to work or perform daily activity.

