7.1.8 Adverse events of special interest

An AESI (serious or non-serious) is one of scientific and medical concern for which ongoing monitoring and rapid communication by the investigator to the sponsor can be appropriate. Adverse events of special interest for this study include QTc prolongation as well as liver tests that meet the criteria for potential drug-induced liver injury (DILI), in accordance with the US Food and Drug Administration "Guidance for Industry-Drug-Induced Liver Injury: Premarketing Clinical Evaluation".

Adverse event of special interest: QTc prolongation

A thorough QT study (PM1116628) was conducted in healthy volunteers who received losmapimod at 7.5 mg BID or 20 mg daily or with placebo administered for 5 days. At the 20 mg dose of losmapimod, the upper bound of the 90% CI of the $\Delta\Delta QT$ interval (change from baseline in QTcF compared with that for placebo) exceeded the 10 msec threshold at the 24-hour post-dose time point. For the 7.5 mg BID dose, the upper bound of the 90% CI of $\Delta\Delta QTcF$ exceeded the 10 msec threshold at multiple time points. No subjects experienced QTcF values >480 msec or QTcF changes from baseline ≥ 60 msec at any time in the study. Although the upper bound of the 90% CI exceeded the 10 msec regulatory threshold of concern in the primary pharmacodynamic analysis, it was determined by GSK that there was no clinically relevant effect on the QT interval, as there was no clinically relevant concentration QTc effect using standard placebo/baseline subtracted measured QTc data. Additional information on the QTc interval and its behavior, as demonstrated in the large cohort of patients with ACS treated with losmapimod (PM1116197), supported the lack of a QT effect. PK/PD modeling using the raw QTcF and plasma concentration data showed that at plasma losmapimod concentrations 4 times the exposure at the therapeutic dose (7.5 mg BID) (ie, at exposures approximately 2-fold higher than 15 mg BID, the predicted upper bound of the 90% CI of $\Delta\Delta QTcF$) did not exceed 10 msec, and the predicted median $\Delta\Delta QTcF$ was less than 5 msec. Further details are presented in the [Investigator Brochure](#). No drug effect on QT prolongation of

Fulcrum Therapeutics
Protocol FIS-001-2020

Losmapimod

Losmapimod over placebo has been documented in any of the phase 2 or the one phase 3 trial completed so far.

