Study drug should be discontinued for subjects who meet the QTc prolongation criteria as a result of within-protocol specific testing or unscheduled testing (see [Section 3.4.4](#) stopping criteria). This AESI must be reported to the sponsor within 24 hours of awareness per the SAE reporting procedures ([Section 7.1.6](#)). Further safety steps should be taken to closely observe and follow-up the event until resolution and treatment initiated per local standard of care.

Adverse event of special interest: Drug-induced liver injury

The following 3 laboratory value criteria must be met for potential DILI, or "Hy's Law":

- An elevated alanine transaminase or aspartate transaminase laboratory value that is $\geq 3 \times$ ULN
- An elevated total bilirubin laboratory value that is $\geq 2 \times$ ULN
- An alkaline phosphatase laboratory value that is $< 2 \times$ ULN

Study drug should be discontinued for subjects who meet the laboratory criteria for potential DILI as a result of within-protocol specific testing or unscheduled testing (see [Section 3.4.4](#) stopping criteria). This AESI must be reported to the sponsor within 24 hours of awareness per the SAE reporting procedures ([Section 7.1.6](#)). Further safety steps should be taken to closely observe and follow-up the event until resolution. These steps include, but are not limited to:

- Making every reasonable attempt to have the subject return to the clinic within 24 hours for repeat liver tests
- Obtaining a more detailed history of symptoms and prior or concurrent disease, concomitant medication use, alcohol use, recreational drug use, and special diets
- Repeating liver enzyme and serum bilirubin tests twice weekly. Frequency of retesting can decrease to once a week or less if abnormalities stabilize and the subject is asymptomatic
- Obtaining viral hepatitis serology
- Considering liver imaging and/or hepatology consultation

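### The SAP plans no by-arm analysis of potential drug-induced liver injury derived from the laboratory data, although the protocol defines that event by three laboratory values

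*SAP*

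**What the plan says.** Protocol 7.1.8 names QTc prolongation and potential DILI as AESIs. For the second it states: "The following 3 laboratory value criteria must be met for potential DILI". The criteria are ALT or AST ≥3 × ULN, total bilirubin ≥2 × ULN and alkaline phosphatase <2 × ULN. Sites must report such a case within 24 hours of awareness.

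Protocol 3.4.1 also uses ULN multiples when it lists reasons to consider stopping study drug: ALT or AST >8 × ULN, >5 × ULN for more than two weeks, and >3 × ULN with either bilirubin or INR elevation or symptoms.

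The analytes are collected. The chemistry panel in Protocol 6.5.5 includes total bilirubin and "alkaline phosphatase, AST, ALT, gamma-glutamyl transferase, and LDH". Safety chemistry is run at local laboratories (Protocol Table 1, footnote 6), and sites must supply those laboratories' normal ranges (Protocol 9.7).

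SAP 3.5.2 plans values and changes from baseline by arm and time point, and says that the number of "available observations and out-of-range values (absolute and in percentage) will also be presented by treatment group". For that summary, "all post-baseline values, including those from unscheduled visits will be evaluated". Protocol 8.5.9 adds no liver-specific display.

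Two other parts of the SAP bear on liver tests. Section 3.5.1 has one overview row by arm for all treatment-emergent AESIs. Section 3.4.2 gives, by arm, the percentage of subjects with clinically significant laboratory changes.

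**The concern.** The protocol fixes an objective laboratory definition for a liver event that the sponsor has singled out, and collects every value needed to apply it. The SAP never applies it. Whether an excess of such cases on losmapimod is visible by arm therefore depends on sites recognising and reporting each case, or judging a result clinically significant.

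The laboratory tables cannot serve as a check on that reporting. An out-of-range flag treats 1.1 × ULN and 10 × ULN alike. Raw U/L changes pool local laboratories with different reference ranges. No table links ALT, bilirubin and alkaline phosphatase in the same subject. As worded, the out-of-range summary also counts values rather than subjects and includes unscheduled draws, so a frequently tested subject could weigh more than one seen weekly after discharge. The SAP does not state the denominator, so the size of that last effect cannot be judged.

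**Working it through.** **1. What each planned output can show**

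| Output | Counts subjects? | Uses a ULN multiple? | Joins ALT/AST, bilirubin and ALP? | Depends on |
|---|---|---|---|---|
| Values and changes (SAP 3.5.2, statistics in 3.1.3) | No | No | No | Raw local units |
| Out-of-range values (SAP 3.5.2) | Not as worded | No | No | Number of draws |
| AESI overview row (SAP 3.5.1) | Yes, and events | Through the 7.1.8 definition, if reported | If reported | Site reporting; pooled with QTc |
| AEs by system organ class and preferred term (SAP 3.4.2) | Yes | No | No | Site reporting and term chosen |
| Clinically significant laboratory changes (SAP 3.4.2) | Yes | No | No | Clinical judgement |

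The last output has two further limits. It needs a baseline that is not clinically significantly abnormal, whereas exclusion criterion 5 (Protocol 4.2) removes only ALT or AST ≥5 × ULN. A subject who enters at 4 × ULN, is judged clinically significantly abnormal, and then rises further would not count. Its denominator is completers plus deaths, not the Safety Analysis Set. The SAP does not say whether it is shown per analyte.

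**2. Illustration of what is lost if sites under-report**

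The documents give no liver event rate, out-of-range rate or reporting rate. Arm size is 205 (Protocol 8.1.1); everything else here is assumed. Suppose 6 of 205 losmapimod subjects (6/205 = 2.9%) and 0 of 205 placebo subjects meet the 7.1.8 definition. The p-values are only a yardstick, because the SAP plans no test on the AESI overview or the 3.5.2 tables.

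- Fisher's exact test, two-sided, on cases counted: 6 vs 0 gives 0.030; 5 vs 0 gives 0.061; 3 vs 0 gives 0.25. A laboratory-derived count stays at 6 vs 0, provided the values were drawn and entered. The AESI count falls with each unreported case.
- Six cases added to a subject-level out-of-range count, with a common rate of 20%, 40% or 60%: 47 vs 41, 88 vs 82 and 129 vs 123 of 205. The two-sided p-values are 0.55, 0.62 and 0.61. This assumes that none of the six would otherwise be out of range; if some would, the contrast is smaller.
- Mean ALT, assuming a rise of 200 U/L in each case: the difference is 6/205 × 200 = 5.85 U/L. The standard error is SD × √(2/205) = 3.95, 5.93 or 7.90 for an assumed SD of 40, 60 or 80 U/L. The ratio is 1.48, 0.99 or 0.74.

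**3. Why single cases matter**

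The chance of at least one case among 205 subjects is 1 − (1 − p)^205. For an assumed true rate of 0.1%, 0.5% or 1% it is 19%, 64% or 87%. Zero cases in 205 gives a two-sided 95% upper limit of 1 − 0.025^(1/205) = 1.8%. Expected counts are small, so a few unreported cases change the picture.

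**The case against.** A reader might infer that liver tests are summarised only as mean changes and out-of-range counts, and that liver injury is therefore never compared by arm. The documents do not support that.

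- SAP 3.4.2 already plans a subject-level, at-least-once comparison of clinically significant laboratory changes by arm, with Clopper-Pearson intervals and a between-arm analysis along the lines of the primary endpoint.
- Reporting of potential DILI is mandatory under Protocol 7.1.8, and SAP 3.5.1 counts AESIs by arm. If sites comply, the six assumed cases appear there in full. The pooling with QTc affects only that overview row, since hepatic and QT terms separate by preferred term.
- Such cases may also appear among adverse events leading to study drug discontinuation.
- The descriptive statistics include quartiles and the maximum (SAP 3.1.3), so an extreme value could be seen.

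A reader might also infer that the AE intensity scale hides symptomless cases, because its top grade reads "Severe: inability to work or perform daily activity". That does not follow: the AESI row is not split by severity, so the grade does not decide whether a case is counted.

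The entry limit should not be overstated either. Values up to just under 5 × ULN are allowed for ALT and AST only; bilirubin >1.5 × ULN is excluded.

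Finally, listings are planned, the DMC may request further reports (SAP section 4), and the detailed programming specifications are a separate document (SAP section 7). An unlisted table is possible, but the SAP does not commit to one.

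All of this stands and narrows the point. None of it derives the 7.1.8 event from the laboratory data.

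**Conclusion.** The point holds in this form: potential DILI is defined by laboratory values, yet no SAP output identifies it, or grades liver tests by ULN multiple, from the laboratory data by arm. Its by-arm visibility rests on site reporting and clinical judgement, with no objective cross-check.

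The 6-vs-0 figures show what could be lost under incomplete reporting. They are not the expected result of the planned analyses, and they depend on the assumed counts: at 5 vs 0 the two-sided p is already 0.061. The primary efficacy inference is unaffected. The change is worth making because the gap concerns a safety event that the sponsor itself named, and it can be closed with existing data.

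A separate inconsistency lies in the same passages. Protocol 7.1.8 says study drug should be discontinued when the potential-DILI criteria are met and refers to 3.4.4, which contains no laboratory criteria. The liver criteria sit in 3.4.1, use different thresholds, and say that discontinuation should be considered. These passages must be reconciled.

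**What to change.** In SAP 3.5.2, add by arm for the Safety Analysis Set the number and percentage of subjects:

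- whose maximum post-baseline ALT or AST crosses the protocol's own 3, 5 and 8 × ULN thresholds, matching its > or ≥ signs (as display categories, without the duration, symptom or INR conditions of 3.4.1);
- whose total bilirubin is ≥2 × ULN;
- who meet the full 7.1.8 combination, stating whether the three values must come from the same draw, on which 7.1.8 is silent.

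Use each local laboratory's ULN and include unscheduled values. Show ALT and AST against baseline category. Report out-of-range results as subjects with at least one such value. In SAP 3.5.1, give DILI and QTc AESIs separate rows.

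The cost is SAP wording and a few tables from chemistry and normal ranges already collected, with no new procedure. The discontinuation passages in Protocol 3.4.1, 3.4.4 and 7.1.8 should be reconciled by those responsible for clinical management; this point does not say which rule should prevail.

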3.5.3 Vital Signs

Reported values and change from baseline values of supine blood pressure and pulse rate and temperature will be summarized using descriptive statistics by treatment group and time point. The number of available observations and out-of-range values (absolute and in percentage) will be presented by treatment group. Vital sign variables will be listed. Values outside the reference range (see [Table 1](#)) will be flagged in the listing.

Table 1: Normal vital sign ranges for the average healthy adult while resting

| Variable | Normal Range |
|--------------------------|-----------------------------------|
| Systolic Blood Pressure | 90 to 120 mm Hg |
| Diastolic Blood Pressure | 60 to 80 mm Hg |
| Breathing | 12 to 19 breaths per minute |
| Pulse | 60 to 100 beats per minute |
| Temperature | 97.8 to 99.1°F (36.5°C to 37.3°C) |

Extended vital signs, including oxygen saturation and fraction of inspired oxygen will also be summarized using descriptive statistics and listed in similar manners as other the vital signs.

